### 3. Research Methods

#### Research Design

This trial will adopt a randomized controlled prospective study design.

#### Inclusion and Exclusion Criteria

##### **Subject Inclusion Criteria are as follows:**

1. Patients who have undergone radical prostatectomy with a clear pathological diagnosis of prostate cancer.
2. One week post-RP.
3. Karnofsky Performance Status (KPS) score  $\geq 60$  or ECOG score 0-1.
4. Age between 50 and 85 years.
5. Signed informed consent.

##### **Subject Exclusion Criteria are as follows:**

1. Pathology report shows positive surgical margins.
2. Has undergone treatment for postoperative urinary incontinence, such as cystostomy, urinary sphincter reconstruction, or urethral sling surgery.
3. Currently receiving or has received treatments with similar principles to acupuncture (e.g., electroacupuncture, moxibustion, warm needling) within the past six months.
4. Patients with urinary tract infections (excluding asymptomatic lower urinary tract infections).
5. Known severe cardiac diseases, such as severe arrhythmia, severe cardiac insufficiency, acute myocarditis, constrictive pericarditis, cardiac tamponade, or severe valvular disease.
6. Known liver damage or potential severe liver disease (ALT or AST  $> 10$  times normal).
7. Known severe renal impairment (eGFR  $< 25$  mL/min/1.73m^2), or planning/undergoing dialysis, or acute contrast-induced nephropathy at screening.
8. Known severe primary diseases in other vital organs or the hematopoietic system.
9. Known coagulation dysfunction (with typical clinical diagnosis or definitive laboratory test results).
10. Patients with psychiatric disorders or cognitive impairment; severe depression, alcohol dependence, or history of drug abuse.

11. Existing urinary incontinence due to other reasons.
12. Patients deemed unsuitable for the study by the investigator, or those with a high probability of dropping out, such as frequent changes in work environment leading to difficulty in follow-up.
13. Life expectancy  $\leq 6$  months, as judged by the investigator.
14. Currently participating in other clinical trials.

### (3) Enrollment and Treatment Protocol

Information on patients who have undergone radical prostatectomy will be obtained from the EMR systems of Zhongda Hospital, Nanjing Lishui People's Hospital, and Wuxi Xishan People's Hospital. After screening patients who meet the inclusion/exclusion criteria and signing the informed consent form, patients will be allocated into groups using a centralized, stratified block randomization method and receive either acupuncture treatment or sham acupuncture treatment.

**Trial Treatment Protocol:** All patients will have their urinary catheter removed on postoperative day 14 (POD 14). The early acupuncture intervention (including real and sham acupuncture) will be initiated on postoperative day 7 (POD 7), with subsequent sessions on POD 9 and POD 11, for a total of 3 sessions.

**Treatment Group:** Receive electroacupuncture at acupoints including Shenshu (BL23), Pangguangshu (BL28), and Baliao (BL31-34), 30 minutes each time. A continuous wave of 2Hz will be used initially, with the intensity gradually increased to a level that is comfortable for the patient. The current intensity will be 1-5mA and can be gradually increased to the maximum tolerable level for the patient.

**Control Group:** Will use non-invasive sham acupuncture needles: validated blunt-tip, non-penetrating needles. When pressure is applied, the needle tip retracts into the handle, giving the patient a sensation of pressure on the skin, but it does not puncture the skin. The procedure will be performed at **non-acupoints** (points 1-2 cm away from the real acupoints but not on the same meridian). The electroacupuncture device clips will also be attached to the sham needle handles, and the device will be turned on (emitting the same sound or light indicators), but **no electrical current will be delivered**. This ensures the entire treatment scenario is visually and auditorily identical to the real treatment group.

To ensure all subjects receive consistent standard postoperative rehabilitation guidance and to control for potential confounding variables, all successfully enrolled patients (regardless of group) will receive standardized Pelvic Floor Muscle Training (PFMT) health education on POD 7 (the same day as the first intervention).

### Efficacy Evaluation

1. **Primary Endpoint:** Urine leakage volume (grams) measured by the first 1-hour pad test during the follow-up at 1 week post-catheter removal.
2. **1-hour Pad Test Results:** Conducted at the 4-week and 24-week follow-ups.
3. **ICIQ-SF Questionnaire Score:** At 1, 4, 8, 12, and 24 weeks post-removal to evaluate incontinence symptoms and their impact on quality of life. The proportion of completely continent patients (zero leakage) will directly quantify immediate continence.
4. **Self-Rating Anxiety Scale (SAS) Score:** To assess the potential improvement in patients' psychological state due to the acupuncture intervention.
5. **Voiding Diary and IPSS:** Patients will maintain a voiding diary and complete the International Prostate Symptom Score (IPSS) questionnaire at each follow-up node to assess nocturia and provide a comprehensive evaluation of urinary function.

#### (4) Statistical Analysis

Statistical analysis will be performed by professional statisticians from the Clinical Evaluation and Analysis Center of Zhongda Hospital, Southeast University, using SPSS Statistics (V.26.0). All analyses will follow the Intention-to-Treat (ITT) principle. Data normality will be assessed using the Shapiro-Wilk test. Imbalances in baseline demographic and clinical characteristics will be adjusted using Analysis of Covariance (ANCOVA). Normally distributed continuous variables will be expressed as mean  $\pm$  standard deviation; non-normally distributed continuous variables and ordinal variables will be expressed as median (interquartile range); categorical variables will be expressed as counts and percentages. Missing data for primary and secondary endpoints will be handled using multiple imputation, and the primary analysis will be based on the imputed dataset. A series of sensitivity analyses will be conducted to assess the robustness of the study conclusions to different methods of handling missing data. After catheter removal (during the 4-week follow-up), the type of urinary incontinence will be classified through clinical assessment (e.g., medical history, cough stress test). An analysis will then be performed to determine if there are differences in the efficacy of early acupuncture intervention in the subgroup of patients "diagnosed with pure stress urinary incontinence" versus other subgroups, such as "mixed urinary incontinence".

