#### Number of subjects to be enrolled at each center:

- Department of Urology, Zhongda Hospital, Southeast University: 84 cases
- Department of Urology, Nanjing Lishui People's Hospital: 30 cases

- Department of Urology, Wuxi Xishan People's Hospital: 30 cases

**Sample Size:** This study is a prospective, multi-center, randomized, placebo-controlled clinical trial designed to assess the efficacy of early electroacupuncture intervention in improving immediate urinary continence after radical prostatectomy (RP). The Primary Endpoint has been determined as the urine leakage volume (in grams) measured by the 1-hour pad test administered immediately after catheter removal (within the first 1 hour post-removal). This calculation is based on a test comparing two independent sample means. The required parameters include the expected mean difference between groups (effect size,  $\delta$ ), the within-group standard deviation ( $\sigma$ ), the Type I error probability ( $\alpha$ ), and the Type II error probability ( $\beta$ ). We set the two-sided significance level  $\alpha = 0.05$ , statistical power  $(1-\beta) = 0.80$ , and a 1:1 allocation ratio for the two groups (treatment vs. sham acupuncture).

In the absence of a perfectly matched study focusing on post-RP males, comparing electroacupuncture versus sham acupuncture, and using the 1-hour pad test (grams) as the primary endpoint, we have, after rigorous screening, selected a high-quality, large-scale ( $N=504$ ), multi-center randomized controlled trial published by Liu et al. in the Journal of the American Medical Association (JAMA) in 2017 as the primary basis for parameter estimation. That study's methodological design (electroacupuncture vs. sham acupuncture) and primary outcome measure (1-hour pad test leakage volume) are highly consistent with our study, representing the best available evidence. Although its study population was women with stress urinary incontinence, we consider its reported effect size and variability data to be the most reasonable reference for this calculation, given the cross-gender commonality of the core physiological mechanism (sacral neuromodulation via electroacupuncture) for regulating urinary control.

Based on the results from Liu et al.'s study:

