- **Expected Effect Size ( $\delta$ ):** The electroacupuncture group showed 7.4 grams more reduction in 1-hour pad test leakage compared to the sham acupuncture group. We use this as the expected mean difference between groups.
- **Within-group Standard Deviation ( $\sigma$ ):** Based on the reported 95% confidence interval of the effect size, we extrapolated the pooled standard deviation for the "change value" in leakage volume (before and after intervention) to be approximately 14.9 grams.

Based on the parameters above, using the sample size formula for comparing two independent means:  $n = [(Z\alpha/2 + Z\beta)^2 \times 2\sigma^2] / \delta^2$

The calculation shows that to achieve 80% power, **each group requires at least 64 subjects.**

Considering the short intervention cycle and clear follow-up nodes of this study, we estimate a dropout or withdrawal rate of approximately 10%. To compensate for this potential sample loss, the adjusted number of recruits needed per group is  $64 / (1 - 0.10) \approx 71.11$ . Rounding up, we determine that **each group needs to recruit 72 subjects**.

In summary, this study plans to enroll a total of **144 subjects** (72 in the treatment group, 72 in the control group). This sample size is sufficient to statistically and effectively test the core hypothesis of this study and is feasible within the multi-center collaborative framework. An interim analysis will assess whether the sample size needs adjustment based on actual enrollment and data variability.

**Reference:** Liu Z, Liu Y, Xu H, et al. Effect of Electroacupuncture on Urinary Leakage Among Women With Stress Urinary Incontinence: A Randomized Clinical Trial. *JAMA*. 2017;317(24):2493–2501. doi:10.1001/jama.2017.7220

**(3) Study Period** 2025.08.01——2027.08.01

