### Study Subject Sampling and Allocation Method

This study will employ a prospective, multi-center, randomized controlled trial design. All patients undergoing radical prostatectomy during the study period who meet all inclusion criteria, do not meet any exclusion criteria, and voluntarily sign the informed consent form will be enrolled consecutively. To ensure the scientific rigor of the allocation process, subject allocation will utilize a **centralized, stratified block randomization** method. We will use participating hospitals as the stratification factor, generating independent random sequences for each center to eliminate potential inter-institutional bias. Within each stratum, we will use mixed block sizes (sizes 4 and 6) for random allocation to maintain a close dynamic balance between the treatment and control groups at all stages of the study. To achieve allocation concealment, the random sequences will be generated by an independent statistician (not involved in clinical work) and deployed within a secure central randomization system. On-site researchers will only be able to obtain the patient's group assignment through the system *after* the patient is formally enrolled, thereby preventing selection bias. This study plans to randomly allocate a total of 144 subjects to the treatment group and the control group in a 1:1 ratio.

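### ANCOVA adjustment is tied to baseline imbalance seen after randomisation, not to hospital and prognostic covariates fixed in advance (minor)

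*Protocol*

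**What the plan says.** The Statistical Analysis section gives one rule for covariates: "Imbalances in baseline demographic and clinical characteristics will be adjusted using Analysis of Covariance (ANCOVA"). It names no other model for comparing the groups. The sentence stands between the normality check and the choice of descriptive summaries, and is not attached to any endpoint. The same section plans multiple imputation and says that "the primary analysis will be based on the imputed dataset".

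The primary endpoint under Efficacy Evaluation is "Urine leakage volume (grams) measured by the first 1-hour pad test during the follow-up at 1 week post-catheter removal".

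On allocation, Study Subject Sampling and Allocation Method says "We will use participating hospitals as the stratification factor", and then "Within each stratum, we will use mixed block sizes (sizes 4 and 6) for random allocation". The sequence is held centrally and concealed until a patient is enrolled.

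The sample size text says "This calculation is based on a test comparing two independent sample means", so the trial is sized on an unadjusted comparison. Its standard deviation is that of a change "in leakage volume (before and after intervention) to be approximately 14.9 grams".

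**The concern.** The sentence is a rule of selection, and so is more than a covariate list left open. It makes a difference between the arms the reason for adjusting. That is the wrong reason in a randomised trial. When allocation is concealed and random, a baseline difference is a chance event. Its presence does not make a variable prognostic, and its absence is no reason to leave out a variable that is. Adjustment improves precision when the covariate explains variation in the outcome, and this can be judged before any patient is allocated.

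The rule also fits poorly with the randomisation. Stratified blocks are there to keep hospital balanced, so a rule that looks for imbalance does not provide for hospital as a term. If hospital predicts leakage, an analysis without it discards part of what stratification offers.

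At stake is efficiency. An SAP that follows the protocol takes over the imbalance rule, and an SAP that fixes prognostic covariates has to override it.

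**Working it through.** **1. The protocol's own figure.** Inputs from the sample size text: difference 7.4 g, SD 14.9 g, two-sided alpha 0.05, power 80%, 1:1 allocation, 10% dropout.

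n = (1.960 + 0.842)² × 2 × 14.9² / 7.4² = 63.6, rounded up to 64 per group. Then 64 / 0.90 = 71.1, rounded up to 72 per group, or 144 in total. The stated figures reproduce.

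**2. What a fixed covariate could add, by formula.** With 64 per group, the standard error of the difference is 14.9 × √(2/64) = 2.634 g. Then 7.4 / 2.634 = 2.809, and power is Φ(2.809 − 1.960) = 80.2%. A covariate that explains a share R² of the outcome variance reduces the SD to 14.9 × √(1 − R²). The protocol gives no R², so the values are assumptions:

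| R² | SD (g) | 7.4 / SE | Power |
|---|---|---|---|
| 0 | 14.90 | 2.809 | 80.2% |
| 0.02 | 14.75 | 2.838 | 81.0% |
| 0.05 | 14.52 | 2.882 | 82.2% |
| 0.10 | 14.14 | 2.961 | 84.2% |

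**3. What the imbalance rule keeps of that gain, by simulation.** Each cell has 10,000 trials: 144 patients (84/30/30) randomised in blocks of 4 and 6 within hospital, 129 kept at random, effect 7.4 g, SD 14.9 g. The fixed model contains hospital and one covariate. The protocol gives no criterion for imbalance, so three triggers were tried: baseline p<0.05, and a standardised mean difference (SMD) above 0.20 or above 0.10. Power in %:

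| Hospital R² | Covariate R² | Fixed | p<0.05 | SMD >0.20 | SMD >0.10 |
|---|---|---|---|---|---|
| 0 | 0 | 80.0 | 80.2 | 80.2 | 80.0 |
| 0 | 0.02 | 80.0 | 79.5 | 79.7 | 79.7 |
| 0 | 0.05 | 82.0 | 80.4 | 80.8 | 81.5 |
| 0 | 0.10 | 83.4 | 80.1 | 81.0 | 82.5 |
| 0.05 | 0 | 81.2 | 80.0 | 79.9 | 80.1 |
| 0.05 | 0.02 | 82.7 | 80.7 | 80.6 | 81.4 |
| 0.05 | 0.05 | 83.4 | 80.4 | 80.8 | 81.8 |
| 0.05 | 0.10 | 85.8 | 80.7 | 82.1 | 83.5 |

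Monte Carlo error is about 0.4 points per cell. At covariate R² 0.10 the gain over the p<0.05 trigger is 83.4 − 80.1 = 3.3 to 85.8 − 80.7 = 5.1 points. Over the SMD >0.10 trigger it is 83.4 − 82.5 = 0.9 to 85.8 − 83.5 = 2.3 points. With nothing prognostic it is 80.0 − 80.2 = −0.2 points, which is no gain. The p<0.05 rule recovers little because one candidate covariate triggers it in only 5% of trials. The SMD triggers fire in 26% (>0.20) and 57% (>0.10).

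**4. Type I error.** In simulation the mechanical triggers gave 2.8% to 5.2% and the fixed model 4.7% to 5.3%, with Monte Carlo error of about 0.2 points. Neither is inflated, and the triggered rule tends to be conservative.

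**5. Hospital.** Among all 144 randomised, hospital was never imbalanced at p<0.05 or at SMD >0.10 in 10,000 allocations. Among the 129 evaluable it was still never flagged at p<0.05, but it exceeded SMD 0.10 in 27% of trials because of random dropout.

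**Limits.** Outcomes are simulated as normal and complete, whereas the plan uses multiple imputation. The 14.9 g is the SD of a change, applied here to a single weight after catheter removal. The catheter stays in until day 14, so no pad test can precede treatment and a baseline value of the outcome is not available as a covariate. That is a reason not to assume a large R².

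**The case against.** The strongest reply is that nothing is broken. The rule keeps alpha, the sample size and the planned power, so what remains is an optional gain that may be nil. **This stands, and it is why the point is minor.** It does not remove the point, because the protocol states a poor principle for choosing covariates where a sound one costs nothing.

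Second, the sentence may not concern the primary endpoint. The sample size rests on an unadjusted comparison, and ANCOVA may be meant as a supportive step. **This reading is open.** But no other comparative model is named, and an adjusted analysis driven by observed imbalance is a weak choice in a supportive role too.

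Third, covariates belong in the SAP. **For the list and the threshold this is right,** and their absence is not criticised here.

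Fourth, nothing in the protocol shows that age predicts leakage. "Age between 50 and 85 years" is an eligibility criterion only. **This stands:** age can be an example, to be used if it is judged prognostic.

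Three stronger readings may tempt a reader, and the documents support none of them:

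- *The rule inflates type I error.* That needs someone to choose between adjusted and unadjusted results after seeing both. In simulation this gives about 6.0% at an assumed covariate-outcome correlation of 0.3 and 7.0% at 0.5. The text does not call for such a choice.
- *The rule could never pick hospital.* This is true of the 144 as randomised under the triggers tried, but not of the 129 evaluable at SMD >0.10.
- *Ten or more power points are lost.* The largest simulated gain, 10.6 points, needs three unnamed covariates with a joint R² of 0.30, hospital R² of 0.05 and the p<0.05 trigger (92.8% against 82.2%). The protocol offers no basis for these values.

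**Conclusion.** The point holds as a minor defect of analysis choice. The protocol makes chance imbalance the ground for adjustment and does not provide for the stratification factor. Validity, sample size and planned power are unaffected if the rule is applied as written.

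The cost is a forgone gain in precision: about zero if the covariates are not prognostic, and about 3 to 5 power points against a p<0.05 trigger at a covariate R² of 0.10 with hospital R² between 0 and 0.05. A looser trigger narrows the difference. All R² values and triggers are assumptions, and the figures are for normal, complete outcomes.

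**What to change.** Replace the ANCOVA sentence with:

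> Adjusted between-group comparisons, including that of the primary endpoint, include hospital (the randomisation stratum) and a short list of baseline covariates chosen for expected prognostic value (for example age, if judged prognostic) and named before unblinding; no covariate is added or removed because of observed baseline imbalance. An unadjusted comparison is reported as a sensitivity analysis.

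Add that the same covariates apply whichever outcome scale or method is used if leakage weights are not normal. The change then does not commit the trial to normal-theory ANCOVA against its own normality check.

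The cost is a few lines of text. Hospital is already the randomisation stratum, and age is already recorded for eligibility. Sample size and visits do not change.

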by surgical trauma.), **Enhancing baseline sphincter tone** (Preemptively increasing the resting tension of the external urinary sphincter through pudendal nerve stimulation.), **Stabilizing detrusor function** (Inhibiting potential, uncoordinated detrusor contractions to prepare for stable bladder filling.), and **Reducing local inflammatory response** (Acupuncture has a recognized anti-inflammatory effect, which can help reduce surgical site edema and nerve irritation, creating a more favorable local microenvironment for functional recovery.) This "pre-emptive" intervention aims to adjust the patient's neuromuscular system to a better state of readiness, enabling it to more effectively cope with the pressure of bladder filling at the moment of catheter removal, thereby achieving a smoother transition in urinary control function and shortening or even avoiding a severe immediate incontinence period.

In summary, the early acupuncture intervention protocol proposed in this study not only possesses a solid neurophysiological basis and ample supporting evidence but also represents a shift in clinical thinking from "passive treatment" to "active prevention." By implementing non-invasive neuromodulation at a critical time window, it is expected to fill a huge gap in current clinical practice and provide a safe, effective, and economical new pathway for improving the immediate postoperative quality of life for prostate cancer patients. The specific objective is: To systematically evaluate the efficacy of early acupuncture treatment by comparing the **treatment group** (early acupuncture + standard care) versus the **control group** (no acupuncture + standard care) in terms of urine leakage volume, proportion of complete continence, pad usage, and patient satisfaction within 24 hours after catheter removal.

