## (7) Treatment Methods

All patients will have their urinary catheter removed on postoperative day 14 (POD14). The early electroacupuncture intervention (including real electroacupuncture and sham electroacupuncture) will be initiated on postoperative day 7 (POD 7), with subsequent sessions on POD 9 and POD 11, for a total of 3 sessions.

**Treatment Group:** Receive electroacupuncture at acupoints including Shenshu (BL23), Pangguangshu (BL28), and Baliao (BL31-34), 30 minutes each time. A continuous wave of 2Hz will be used initially, with the intensity gradually increased to a level that is comfortable for the patient. The current intensity will be 1-5mA and can be gradually increased to the maximum tolerable level for the patient.

**Control Group:** Will use non-invasive sham acupuncture needles: validated blunt-tip, non-penetrating needles (such as Park or Streitberger needles). When pressure is applied, the needle tip retracts into the handle, giving the patient a sensation of pressure on the skin, but it does not puncture the skin. The procedure will be performed at **non-acupoints** (points 1-2 cm away from the real acupoints but not on the same meridian). The electroacupuncture device clips will also be attached to the sham needle handles, and the device will be turned on (emitting the same sound or light indicators), but **no electrical current will be delivered**. This ensures the entire treatment scenario is visually and auditorily identical to the real treatment group.

To ensure all subjects receive consistent standard postoperative rehabilitation guidance and to control for potential confounding variables, all successfully enrolled

patients (regardless of group) will receive standardized Pelvic Floor Muscle Training (PFMT) health education on POD 7 (the same day as the first intervention).

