## Expected Research Outcomes

This study anticipates that early acupuncture intervention will significantly improve immediate urinary continence in post-RP patients after catheter removal. This is expected to manifest as reduced urine leakage volume, an increased proportion of complete continence, decreased pad usage, and enhanced patient satisfaction. If the study results confirm these expectations, it will provide a new, non-invasive intervention for clinical practice, significantly improving the quality of patients' postoperative recovery and reducing the burden on the healthcare system. This study will directly address the core issue of generally low-quality evidence in this

field by employing a gold-standard research design, focusing on the POD 7-14 window—a period not yet systematically studied—to explore the impact of early acupuncture intervention on immediate continence upon catheter removal. It is expected to provide high-level evidence for improving the early postoperative quality of life for prostate cancer patients. Furthermore, this study will promote the integration of traditional Chinese medicine with modern medicine, providing new therapeutic ideas and practical evidence for post-prostatectomy urinary incontinence rehabilitation globally.

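### The one named subgroup analysis sorts men by an incontinence type diagnosed four weeks after catheter removal, which treatment is expected to influence, so it is not a randomised comparison

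*Protocol*

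**What the plan says.** Protocol section (4) Statistical Analysis sets the timing: "After catheter removal (during the 4-week follow-up), the type of urinary incontinence will be classified through clinical assessment". It goes on: "An analysis will then be performed to determine if there are differences in the efficacy of early acupuncture intervention in the subgroup of patients" with pure stress incontinence, set against other groups such as mixed incontinence. The same section puts every analysis under intention-to-treat. It names no endpoint for this comparison and attaches no caveat to it. No other subgroup analysis is named in the protocol.

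Treatment is finished long before that visit. Section (7) Treatment Methods starts the sessions on POD 7, "with subsequent sessions on POD 9 and POD 11, for a total of 3 sessions", and removes the catheter on POD 14.

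The Rationale gives the routes by which treatment should work. For the sphincter it proposes "Preemptively increasing the resting tension of the external urinary sphincter through pudendal nerve stimulation". For the detrusor it proposes "Inhibiting potential, uncoordinated detrusor contractions to prepare for stable bladder filling". Expected Research Outcomes anticipates "reduced urine leakage volume, an increased proportion of complete continence".

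**The concern.** A subgroup comparison keeps the protection of randomisation only if the subgroup is fixed before treatment, or at least cannot be altered by it. Here the classifying variable is observed after all treatment. It is also built from the two functions that the protocol says treatment acts on, the sphincter and the detrusor.

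Two things can follow. A man whom treatment makes dry by week 4 has, on the natural reading, no incontinence type and leaves the comparison. And if mixed means stress plus an urge component, a man whose detrusor is calmed can pass from mixed to pure stress. In either case the treated men in a type differ in prognosis from the control men in the same type.

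At stake is any statement that early acupuncture works better, or worse, in one type. It could understate the effect within a type, or reflect who changed category rather than who benefits.

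**Working it through.** **Order of events (protocol dates).** Last session: POD 11. Catheter removal: POD 14. Four-week visit: 14 + 28 = POD 42. Gap from the last session: 42 − 11 = 31 days, or 31/7 = 4.4 weeks. The primary endpoint in Outcome Measures is at week 1 after removal (POD 21), so if that is the endpoint compared, the subgroup is defined three weeks after the outcome.

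**The protocol's own figures.** With δ = 7.4 g, σ = 14.9 g, two-sided α = 0.05 and 80% power, n = (1.960 + 0.842)² × 2 × 14.9² / 7.4² = 63.6, so 64 per group. Then 64/0.90 = 71.1, so 72 per group and 144 in total. These reproduce, and this point does not alter them.

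The protocol gives nothing from which to compute the bias. The three illustrations below rest on assumed values. They show direction and plausible order of size only.

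**Illustration A: type depends on two latent deficits.** Every treated man gains exactly 7.4 g and the SD is 14.9 g. A shared prognostic factor U drives leakage (20 + 10U + noise of SD 11), a sphincter deficit (0.5 + 0.6U + noise of SD 0.8) and a detrusor deficit (−0.2 + 0.6U + noise of SD 0.8). Pure stress means only the sphincter deficit is above 0, mixed means both are, and dry means neither is. There were 2,000,000 simulated men per row.

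| Treatment lowers sphincter / detrusor deficit by | Pure stress, treated vs control | Dry, treated vs control | Difference in pure stress (g) | Difference in mixed (g) |
|---|---|---|---|---|
| 0 / 0 | 35% vs 35% | 23% vs 23% | −7.32 | −7.39 |
| 0.3 / 0 | 28% vs 35% | 30% vs 23% | −6.45 | −6.74 |
| 0.5 / 0 | 23% vs 35% | 35% vs 23% | −5.79 | −6.15 |
| 0 / 0.3 | 44% vs 35% | 26% vs 23% | −6.53 | −6.33 |
| 0 / 0.5 | 49% vs 35% | 27% vs 23% | −5.92 | −5.50 |
| 0.5 / 0.5 | 33% vs 35% | 42% vs 23% | −4.30 | −4.52 |

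The difference in all randomised men stays at −7.4 g in every row. If treatment leaves type alone, there is no bias. Otherwise both within-type effects shrink.

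**Illustration B: men move from mixed to pure stress.** Assume half the control men are of each type, with control means a (pure stress) and b (mixed), a true benefit of 7.4 g in both, no floor, and a share q of treated mixed men labelled pure stress. The apparent effect in pure stress is a − [0.5(a − 7.4) + 0.5q(b − 7.4)] / (0.5 + 0.5q); in mixed it stays 7.4. For a = 14, b = 20, q = 0.2: 14 − (3.30 + 1.26)/0.60 = 14 − 7.60 = 6.40 g.

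| a, b (g) | q = 0.1 | q = 0.2 | q = 0.3 | False difference between types (g) |
|---|---|---|---|---|
| 14, 20 | 6.85 | 6.40 | 6.02 | 0.5, 1.0, 1.4 |
| 12, 22 | 6.49 | 5.73 | 5.09 | 0.9, 1.7, 2.3 |
| 17, 17 | 7.40 | 7.40 | 7.40 | 0 |

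**Illustration C: dry men leave.** Control leakage is gamma with an assumed mean of 17 g (equal to the 408.0 mL per day cited in the Rationale divided by 24, a first-week figure). Treated leakage is max(X − 7.4, 0). Effect in all men versus effect among those still leaking:

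| SD (g) | Treated men dry | All men (g) | Leakers only (g) |
|---|---|---|---|
| 12.0 | 22% | 6.8 | 4.0 |
| 14.9 | 30% | 6.3 | 1.8 |
| 17.0 | 35% | 6.0 | 0.0 |
| 24.0 | 49% | 4.9 | −6.7 (apparent harm) |

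The SD of 14.9 g is the protocol's figure, but there it is an SD of change.

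**B and C together** (a = 14, b = 20, overall SD 14.9, floor at 0, q = 0.2; 3,000,000 draws per scenario): the true effects are 6.2 and 6.6 g and the apparent effects 0.9 and 2.4 g. The difference between types is 0.4 g true and 1.4 to 1.5 g apparent.

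**The case against.** - **Inference, not text.** No passage says that treatment changes incontinence type. The Rationale offers pathways that may operate, and the expected gain in complete continence concerns the period just after catheter removal. This is fair, and the size of any movement is unknown. But those pathways act on the functions that define type, and the trial cannot both rest on them and assume they leave type unchanged.
- **Dry men may still be classified.** The assessment includes medical history, and the list of other subgroups is open-ended. This stands as a possibility. It would weaken the loss of dry men but not the movement between types.
- **Illustration C is not the planned comparison.** It has no types and conditions on pad weight above zero, and the apparent harm arises only under the most skewed distribution tried. This stands: C shows one mechanism and does not forecast the result.
- **The bias between types is small against the noise.** With SD 14.9 g, 64 evaluable men per arm and an even split of types, the standard error of the between-type difference is 14.9 × √(4/32) = 5.3 g, a 95% half-width of about 10.3 g. The largest figure in B, 2.3 g, is under half a standard error, and in A the two types differ by only about 0.4 g at most. This stands. Understatement within each type is the better supported risk.
- **Detail for the analysis plan.** The endpoint and an exploratory label could sit in a SAP. The protocol, however, itself fixes when type is set and that efficacy is compared across it, and that rule is what is at fault.
- **Type cannot be known earlier.** The catheter stays in until POD 14 and existing incontinence is an exclusion. That is true, but it means the question has no randomised subgroup answer here. It does not make this analysis valid.

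**Conclusion.** The concern holds. Week-4 type is a post-treatment variable that the protocol's own mechanisms would alter, so comparing efficacy across it lacks the protection of randomisation, and nothing elsewhere in the protocol repairs or labels this. That conclusion needs only the dates and the stated mechanisms.

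The size is uncertain. It is nil if treatment leaves type unaffected, and material within types if treatment works on both components as hoped. Every figure beyond the 7.4 g and 14.9 g inputs is an assumption. The damage is confined to this one secondary analysis; the other endpoints are not affected. It should be corrected, but it does not threaten the trial's main result.

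**What to change.** Replace the closing sentence of section (4) Statistical Analysis with wording such as:

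> *Week-4 status (dry, pure stress, mixed or other) will be reported as an outcome by arm in all randomised men. Any table of leakage by week-4 type is descriptive and non-randomised, and no efficacy claim will be drawn from it.*

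If subgroup efficacy is wanted, use factors fixed before randomisation, for example hospital, age, and surgical details if they are recorded. Test the treatment-by-subgroup interaction in the full intention-to-treat set and label it exploratory. These factors do not answer the question about incontinence type, and the protocol should say so.

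The cost is analysis wording only, with no new data or visits. The sponsor gives up a by-type efficacy claim and keeps the descriptive table. The change is best made before any outcome data by arm are seen.
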